### ***Source Imaging***

To obtain the subject's anatomical information for source modeling, native-space structural MRI data will be segmented using the research software, BrainSuite [70] (<http://brainsuite.org/>), to generate a cortical surface with a resolution of ~15,000 triangular vertices and imported into Brainstorm for further analysis. We will estimate empirical covariance statistics from the empty-room recordings, to characterize instrument and environmental noise. The noise covariance estimates will use for subsequent inclusion into the imaging estimator of distributed cortical currents. Source analysis will utilize a boundary element model to compute the forward model with lead fields determined from elementary current dipoles distributed perpendicular to each individual's segmented and tessellated cortical surface. We will apply the source modeling method, the minimum norm imaging (sLORETA) algorithm, to the ERFs. To obtain the most meaningful dipoles only source amplitudes of  $\geq 3.2$  nanoAmpere-meter (nAm) will be selected. Dipoles meeting the above selection criteria will place on the subject's MRI coregistered to the anatomic landmarks recorded during MEG collection.

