## **Abbreviations**

ACH	Arkansas Children's Hospital
ACMEGS	American Clinical Magnetoencephalography Society
AE	Adverse Event
AEF	Auditory Evoked Field
APR	Annual Progress Report
CFR	Code of Federal Regulations
CRF	Case Report Form
CT	Computerized Tomography
dB	Decibel
DOB	Date of Birth
ECD	Equivalent Current Dipole
ECG	Electrocardiogram
EEG	Electroencephalography
EOG	Electrooculogram
ERF	Evoked Response Field
FDA	US Food and Drug Administration
fMRI	Functional Magnetic Resonance Imaging
HIPAA	Health Insurance Portability and Accountability Act
HPI	Head Position Indicator
kHz	Kilo Hertz
IAT	Intracarotid Amobarbital Test
ICF	Informed Consent Form
ICH GCP	International Council for Harmonisation Good Clinical Practice
IIR	Infinite Impulse Response
IRB	Institutional Review Board
ISI	Inter-Stimulus Interval
LCD	Liquid Crystal Display
MEG	Magnetoencephalography
MRI	Magnetic Resonance Imaging
MRN	Medical Record Number
MSR	Magnetically Shielded Room
nAm	NanoAmpere-Meter
msec	Millisecond
ORRA	Office of Research Regulatory Affairs
PET	Positron Emission Tomography
PI	Principal Investigator
s	second
SAE	Serious Adverse Event
SD	Standard Deviation
sLORETA	Standardized Low Resolution Brain Electromagnetic Tomography
SPL	Sound Pressure Level
SQUIDs	Superconducting Quantum Interference Devices
SSP	Signal-Space Projection
UADE	Unanticipated Adverse Device Effect
UAMS	University of Arkansas for Medical Sciences
UPIRTSO	Unanticipated Problem Involving Risks to Subjects or Others
VSWM	Visuospatial Working Memory
WM	Working Memory

Title: Pediatric Language and Memory Mapping in Refractory Epilepsy using Magnetoencephalography

PI: [name]

Site: Arkansas Children's Hospital

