### ***Statistical Analysis***

Overall: MEG and clinical parameters will be summarized as means, SD and ranges (for continuous and count data), as proportions (for binary and nominal data), or as proportions supplemented with mean scores (for Likert-scaled or other ordinal data). We will export the MEG

Title: Pediatric Language and Memory Mapping in Refractory Epilepsy using Magnetoencephalography

PI: [name]

Site: Arkansas Children's Hospital

source analysis parameters for further statistical analysis. This is a pilot study that will provide the preliminary sample size estimates to support future research.

**Hemispheric dominance:** Estimation of hemispheric dominance for language [69] and memory [68] will be calculated as the degree of activation of each hemisphere during performance of the task. We will derive an estimate of hemispheric dominance by calculating the difference in activation levels between the hemispheres.

**Group level:** For this pilot [research](#) study, we will perform a preliminary statistical analysis by comparing MEG source activations between hemispheres (left vs. right) with  $\alpha=0.05$  significance level using a research statistical software.

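### The fixed 3.2 nAm source cut has no stated basis, does not match the standardised map the plan names, and may keep few or no sources

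*Combined protocol and SAP*

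**What the plan says.** The relevant text is in Data Analysis of the combined protocol and SAP.

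- **Estimator (Source Imaging).** "We will apply the source modeling method, the minimum norm imaging (sLORETA) algorithm, to the ERFs". The Abbreviations list expands sLORETA as "Standardized Low Resolution Brain Electromagnetic Tomography". The same section describes the method as an "imaging estimator of distributed cortical currents" and sets the cortical surface at about 15,000 vertices.
- **Selection (Source Imaging).** "To obtain the most meaningful dipoles only source amplitudes of" 3.2 nAm or more are to be kept.
- **Use of what is kept (Source Imaging).** "Dipoles meeting the above selection criteria will place on the" subject's MRI. No other use is given.
- **Outcome (Statistical Analysis).** The plan exports the "source analysis parameters for further statistical analysis". On dominance it says: "We will derive an estimate of hemispheric dominance by calculating the difference in activation levels between the hemispheres". A group comparison of left against right follows at alpha 0.05. It does not say whether selected or all sources enter these steps.

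**The concern.** A cut in nAm is a statement about physical dipole moment. It suits a model in which one dipole carries the whole moment of an active area, such as the equivalent current dipole described in Background and Rationale. The plan instead names a distributed, standardised estimator. There the activity is spread over thousands of vertices and each value is rescaled by a factor specific to that vertex, so 3.2 nAm no longer has its usual meaning.

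Two things are at stake. First, two analysts could cut different maps of the same recording (the minimum-norm currents or the sLORETA values) and keep different sources. Second, on either map a fixed value may lie above most or all of the estimated amplitudes and leave nothing to display. If the kept sources also feed the dominance estimate, that estimate inherits both problems.

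**Working it through.** **1. The plan's own figure.** The value 3.2 nAm cannot be reproduced. It appears once, with no noise level, percentile, baseline distribution or citation. References 68 and 69 are attached to the epoch window (Preprocessing; both references) and to hemispheric dominance (Statistical Analysis), not to the cut.

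**2. Which map could be cut.** Write G for the lead field, C for the noise covariance, y for the sensor data and λ for the regularisation.

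- Minimum-norm current: J = G'(GG' + λC)⁻¹y. This is in nAm. A finer mesh adds columns to G, so the same field is shared among more vertices and each receives less. A larger λ also shrinks J.
- Resolution-standardised (sLORETA) value: J_i / √R_ii, with R = G'(GG' + λC)⁻¹G. R_ii has no unit, so the result is formally in current units, but it is rescaled vertex by vertex and is not a dipole moment.
- Variance-standardised value: J_i divided by its own standard deviation. This has no unit.

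The phrase about distributed cortical currents points to the first map and the sLORETA label to the second or third. The plan does not tie the cut to any of them.

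**3. Does the choice of map matter?** This was checked by simulation. Every setting is an assumption: spherical head, about 100 radial sensors, 1,500 fixed-orientation sources, 20 fT noise, a superficial left source of 20 nAm, a deeper right source of 30 nAm, and 200 runs at each regularisation SNR of 1, 3 and 10.

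- The ratio of the sLORETA to the minimum-norm value ran, from 5th to 95th percentile of sources, from 4.6 to 48.8 (SNR 1), 3.0 to 42.9 (SNR 3) and 2.1 to 38.7 (SNR 10). At SNR 3 that is a spread of 42.9 / 3.0 = 14.3-fold, so no single rescaling of 3.2 gives the same selection on both maps.
- With the strongest 5% kept on each map, the mean overlap of the two sets (Jaccard) was 0.25 to 0.27.
- At 3.2 nAm on the minimum-norm map, the median number of sources kept was 0, and the most in any run was 3.

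**4. Does mesh density matter?** Using the same simulated head at SNR 3, without noise, the median peak minimum-norm estimate for a 20 nAm source was:

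- 500 sources: 1.91 nAm
- 1,000 sources: 1.11 nAm
- 1,500 sources: 0.78 nAm

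Tripling the number of sources lowered the peak by a factor of 1.91 / 0.78 = 2.4, with the true source unchanged.

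**5. At the plan's own mesh size.** A further simulation, again with assumed 20 and 30 nAm sources, used 15,000 vertices.

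- Minimum-norm map: median peak 0.09 to 0.43 nAm. The cut is 3.2 / 0.43 = 7.4 to 3.2 / 0.09 = 35.6 times the peak.
- Resolution-standardised map: median peak 1.3 to 2.9. The cut is 3.2 / 2.9 = 1.1 to 3.2 / 1.3 = 2.5 times the peak.

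The typical run kept no source on either map.

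**6. Where the kept sources go.** Source Imaging sends them to the MRI. Statistical Analysis speaks of source parameters and activation levels and does not refer back to the selection. The link may exist, but it is not written.

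**The case against.** The strongest reply has four parts.

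- **The text says minimum norm as well as sLORETA, and nAm suits a current map.** This stands as far as it goes. A reader might infer a flat contradiction of units, and the documents do not support that: one form of standardisation is formally in current units, and the current-map reading is open. But that reading does not rescue the cut, because on that map the amplitude depends on mesh and regularisation, and the plan does not say that this is the map to be cut.
- **Nothing says the selected dipoles enter the statistics.** This stands. A reader might infer that the cut biases the left-right difference, the test at alpha 0.05, or the sample-size estimates meant for later research. None of these follows from the text. The plan also cites sources for its dominance method, whose content is not available here.
- **The simulations are not this study.** This stands. They use point sources, a spherical head and about 100 sensors, against the 306 in the plan, and their values move with the settings. Even there, the sign of the left-minus-right count of kept sources differed between maps in only 3.5% to 11% of runs. A reader might infer that this trial will lose its sources; without amplitudes in the documents, that cannot be said.
- **This is a small pilot, its test is called preliminary, and the memory data will not guide surgery.** This limits the harm. It does not remove the need for a usable rule, because Aim 1 is whether these functions can be measured at all.

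**Conclusion.** The concern holds in this form: the selection rule is a fixed dipole-moment cut without a stated basis, placed after a standardised distributed estimator to which it does not naturally apply. This is more than missing detail, because the rule as written can fail on each map it might be meant for. It does not match a standardised scale, and on a minimum-norm map it depends on mesh density and regularisation and may keep few or no sources.

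The size in this trial cannot be given. The simulated figures rest wholly on assumed inputs and show direction only. The certain consequence is that the sources placed on the MRI are not determined by the plan. If the same sources feed the dominance estimate and the group comparison, the consequence extends to those results; if all sources are used there, it stops at the display. The plan should be corrected before analysis, but this is not a fault in the design or the data collection.

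**What to change.** **Source Imaging.** Name the map to which the cut applies. Replace the 3.2 nAm rule with a cut in that map's own units, set relative to the pre-trigger baseline or the resting-state source imaging already planned under Preprocessing. Take the reference over both hemispheres together, so that the cut is identical left and right, and fix its value before the data are examined.

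**Statistical Analysis.** Name one main dominance value in advance, state whether it uses selected or all sources, and report the value from the uncut map beside it as a sensitivity analysis.

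**Cost.** New wording and a little more analysis of the same recordings; no new data. The uncut value includes background activity and may show a smaller asymmetry, which is why the main value must be named beforehand.

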### ***Statistical Analysis***

Overall: MEG and clinical parameters will be summarized as means, SD and ranges (for continuous and count data), as proportions (for binary and nominal data), or as proportions supplemented with mean scores (for Likert-scaled or other ordinal data). We will export the MEG

Title: Pediatric Language and Memory Mapping in Refractory Epilepsy using Magnetoencephalography

PI: [name]

Site: Arkansas Children's Hospital

source analysis parameters for further statistical analysis. This is a pilot study that will provide the preliminary sample size estimates to support future research.

**Hemispheric dominance:** Estimation of hemispheric dominance for language [69] and memory [68] will be calculated as the degree of activation of each hemisphere during performance of the task. We will derive an estimate of hemispheric dominance by calculating the difference in activation levels between the hemispheres.

**Group level:** For this pilot [research](#) study, we will perform a preliminary statistical analysis by comparing MEG source activations between hemispheres (left vs. right) with  $\alpha=0.05$  significance level using a research statistical software.

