
Advances in technology over the past decade have enabled researchers to study the functional development of the human brain with MEG, a novel and non-invasive technique with fine temporal and spatial resolution. While other modalities infer brain function indirectly (i.e. positron emission tomography (PET), computerized tomography (CT), MRI) by measuring changes in blood flow, cerebral metabolism and blood oxygenation, MEG records neuronal and synaptic function directly. MEG records the tiny biomagnetic fields generated by ionic currents generated by populations of synchronously activated neurons in the brain [8]. Evoked responses fields (ERF) measured with MEG, much like event-related potentials in electroencephalogram (EEG), are waveforms representing variations of brain activity across time following the onset of an external stimulus (auditory, visual, etc.). Early components of the ERF waveform (150-200 msec after stimulus onset) reflect neurophysiological activity in primary sensory cortices. On the other hand, neurophysiological activity represented by later components of the ERF waveform occurs primarily in association cortices. By estimating the regions that contribute to systematic variations in the late components of the ERF, we can study the brain circuits responsible for cognitive and linguistic functions. MEG signal arises from brain sources also seen using electrical signals recorded as the EEG. However, MEG is unaffected by scalp, skin and, to a large degree, brain tissue in homogeneities and is, therefore, an ideal technology to study brain development. MEG is one of several diagnostic techniques employed for the evaluation of patients with epilepsy and it is especially important for those patients being considered for epilepsy surgery [9, 10]. Resective

Title: Pediatric Language and Memory Mapping in Refractory Epilepsy using Magnetoencephalography

PI: [name]

Site: Arkansas Children's Hospital

epilepsy surgery is performed mainly in the temporal and frontal lobes (selective amygdalohippocampectomies, anterior temporal lobectomies, or tailored temporal or frontal corticectomies). However, it must be previously determined that the resection will not have any substantial consequences on cognitive functions, such as language or memory.

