fMRI is the most widely used of the minimally/non-invasive techniques for presurgical language mapping in children [11]. However, MEG is gaining increasing acceptance as a non-invasive method as an adjunctive part of the pre-surgical functional mapping procedure [12]. Especially for language identification in pediatric cases, the quiet environment of the MEG room and the head-motion-tracking methods available in recent MEG systems, increase the likelihood of success with language lateralization in young populations. Further, MEG allows examining both hemispheres simultaneously, which is especially useful in epileptic populations, in which language lateralization is more variable. MEG language localization studies have shown encouraging results with a wide variety of paradigms, especially in localization of receptive language areas that are well documented [13, 14] and validated [15, 16]. The suitability of MEG language lateralization protocols in adults as an alternative to the Wada procedure have been addressed with validation studies conducted using various methodologies and exhibit overall high concordance rates (about 86-92%) [17-20]. Language lateralization is calculated in both hemispheres by localizing dipole sources (equivalent current dipole, ECD model) accounting for late auditory evoked field (AEF) components (150-700 ms after stimulus onset). These late components localize to language-related areas (mainly within posterior temporal areas) of the brain regardless of the modality of stimulus presentation [21]. Depending on the activation task, the dipole sources can be used to identify the location of receptive (Wernicke's area) or expressive language-specific (Broca's area) cortex. The degree of hemispheric asymmetry in the duration or strength of activation can also be calculated as an index of hemispheric dominance for language functions. Estimations of language lateralization with MEG [22] have mainly been based on recognition memory tasks for spoken words [23] or by listening to synthesized vowel sounds [24]. Thus, most of the MEG language studies have focused on receptive language areas. However, other reports exist on frontal circuits in expressive language [25-27] and basal temporal areas during semantic language tasks (verb generation) [28, 29]. Recent MEG language studies have reported the feasibility of passive paradigms in children and adolescents under sedation [30] and during sleep [31]. A recent MEG study [32] uses a verbal memory and verbal fluency tasks showing activation of the left hippocampus and in Wernicke's area in favor of the left hemisphere. Authors found higher concordance rates between a verbal memory paradigm and language dominance in controls (using handedness as criterion) and in subjects with epilepsy (using fMRI or Wada as criterion), compared with a verbal fluency task. Only the concordance for verbal memory reached statistical significance, with 93% agreement. Previous studies in pediatric epilepsy have shown atypical language lateralization [33] and that the word recognition task is the only language comprehension task used in both children and adults that yields high concordance between MEG and the Wada test for language lateralization [22]. Despite all contributions of MEG in the assessment of language localization in typically developing individuals, studies in pediatric populations with epilepsy is still relatively small especially in single subjects, which is necessary for clinical utility.

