### **Aim 2**

Characterize language and memory circuitry in pediatric epilepsy subjects with seizure focus from the right or left hemispheres.

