## **Data Analysis**

### ***Preprocessing***

MEG data will be exported for further analysis from the acquisition computer to the signal processing research software, Brainstorm [66] (<https://neuroimage.usc.edu/brainstorm/>), which is an open-source application dedicated to the analysis of brain recordings. Next, data will band-pass filtered between 0.5Hz to 100Hz and a notch filter will be applied for power-line noise removal (60Hz, 2nd order IIR notch filter with zero-phase lag). We will perform visual inspection to mark bad channels and segments. Data will be preprocessed for eye-blink and electrocardiogram reduction using a signal-space projection (SSP) technique [67]. The corresponding triggers recorded during acquisition will be used to import MEG epochs in the time window ranging from -200s to +800s with respect to the trigger [68, 69]. Baseline correction will be applied on the 200s before the trigger. Next, we will average across epochs to obtain an ERF waveform per subject for the language and memory tasks. Resting state data will use for baseline source imaging.

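### Individual dominance is an unnormalised left-right difference: if activation is an amplitude, its size tracks response strength, and the language window and region are not carried into the analysis

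*Combined protocol and SAP*

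**What the plan says.** In the combined protocol and SAP, the Statistical Analysis section bases hemispheric dominance on how strongly each hemisphere is activated during the task. It cites one reference for language and one for memory, and continues: "We will derive an estimate of hemispheric dominance by calculating the difference in activation levels between the hemispheres". It states no divisor, unit or activation measure. The group-level paragraph compares left with right source activation at a 0.05 significance level.

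Two uses of the dominance values follow from the text. The same section says "This is a pilot study that will provide the preliminary sample size estimates to support future research". Aim 2 is to "Characterize language and memory circuitry in pediatric epilepsy subjects with seizure focus from the right or left hemispheres", with no test between the two focus groups specified.

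For language, Background and Rationale is more specific. It ties lateralization to "late auditory evoked field (AEF) components (150-700 ms after stimulus onset", adds that "These late components localize to language-related areas (mainly within posterior temporal areas) of the brain", and mentions an index built on "hemispheric asymmetry in the duration or strength of activation". It also says: "Early components of the ERF waveform (150-200 msec after stimulus onset) reflect neurophysiological activity in primary sensory cortices".

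In Data Analysis, the only time range is the whole epoch. The only spatial definition is the segmented cortical surface, with a 3.2 nAm cut-off for selecting dipoles. Preprocessing marks bad channels and segments by visual inspection, and then "we will average across epochs to obtain an ERF waveform per subject for the language and memory tasks". The Receptive Language Task section mixes five target words with 40 distractors in each of three blocks, and asks for a finger lift with the dominant hand at each target.

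**The concern.** A plain difference carries two things at once: how asymmetric a subject is, and how strong that subject's response is overall. If response strength varies between subjects for reasons unrelated to language or memory organisation, two equally lateralised subjects receive different degrees of dominance. Two uses are exposed: describing left-focus and right-focus patients side by side under Aim 2, and passing an SD on to the planning of a later study.

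The language measure is also left wider than the plan's own rationale for it. Without a window and region, the value could include early sensory activity, areas outside the language region, and activity from the finger movement.

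**Working it through.** The plan gives no figure for this point, so there is nothing of its own to reproduce. It also gives no amplitudes. Steps 1, 2 and 4 are algebra with illustrative values. Step 3 and parts of steps 5 and 6 rest on assumptions, which are stated.

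**1. Scaling.** Write L = k·l and R = k·r, with k common to both hemispheres. Then L-R = k(l-r), while LI = (L-R)/(L+R) = (l-r)/(l+r), which does not contain k.
- Total 100, split 60:40: L-R = 20, LI = 20/100 = 0.20.
- Total 300, same split (180:120): L-R = 60, LI = 60/300 = 0.20.

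The sign of L-R is the same for every positive k.

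**2. Order of subjects.** A 70:30 split at total 100 gives L-R = 40 and LI = 0.40. A 57:43 split at total 300 gives L-R = 14 × 3 = 42 and LI = 0.14. The raw difference ranks the less lateralised subject higher.

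**3. What this could do to an SD (assumed values).** Take LI with mean 0.2 and SD 0.25, and an independent lognormal total with mean 1 and coefficient of variation CV. The SD of the raw difference is sqrt[(0.0625 + 0.04)(1 + CV²) - 0.04], and the share of its variance due to signal strength is 1 - 0.0625/SD².

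| CV | SD of raw difference | Share from signal strength | Pairs ranked differently from LI | n, one-sample t test, 80% power |
|---|---|---|---|---|
| 0.2 | 0.26 | 6% | 7.3% | 16 |
| 0.5 | 0.30 | 29% | 15.7% | 20 |
| 1.0 | 0.41 | 62% | 23.5% | 35 |

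For LI itself the SD is 0.25 and n is 15 (two-sided 0.05 throughout). The ranking column comes from 2,000,000 simulated pairs per CV, with LI limited to between -1 and 1.

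**4. Limit of the ratio.** Absolute amplitudes contain a positive noise floor. It cancels in L-R if equal on both sides, but stays in the denominator of LI. With the 60:40 split and an assumed floor of 50 per side:
- total 100: (110-90)/(110+90) = 0.10;
- total 300: (230-170)/(230+170) = 0.15.

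So an uncorrected LI is pulled toward zero, and more so in the weaker-signal subject. The planned baseline correction of the epochs removes a mean offset. It does not remove the floor left when noise is taken as an absolute value.

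**5. Window.** Reading the printed epoch limits as milliseconds (an assumption), 150-700 ms covers 550 of the 800 ms after the trigger, or 69%. An asymmetry confined to that window shrinks to 0.69 of its size if averaged over 0-800 ms. The Background's own sensory interval, 150-200 ms, is 50/550 = 9% of the language window. If that activity is symmetric and 1 to 3 times the late level (assumed), it carries 50a/(50a+500) = 9% to 23% of the signal, and a true LI of 0.20 becomes 0.18 to 0.15.

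**6. Target epochs.** If each target occurs once per block, there are 3 × (5+40) = 135 epochs, of which 15 (11%) are targets and 120 distractors. Suppose the movement adds m = k × (15/135) × f × leakage to one hemisphere and the two sides are otherwise equal, so that LI shifts by m/(2+m). With the motor source at k = 1 to 2 times the hemispheric level and f = half to all of it inside the epoch (assumed), the shift is 0.03 to 0.10 over a whole hemisphere. With an assumed 20% leakage into a posterior temporal region it is 0.005 to 0.02. Using distractors only raises noise by sqrt(135/120) = 1.06, about 6%.

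**The case against.** The strongest reply is that the plan cites references for the dominance estimate and follows a published clinical protocol for the language task. These may define a normalised index, a window and a region. That stands: what is shown is that the plan does not write them down, and that a reader following the text computes a raw difference.

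The scaling argument also needs an amplitude measure. If degree of activation meant duration, a common amplitude factor would not multiply the difference one-for-one. That stands too, and the conclusion is conditional on it.

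The table in step 3 treats LI as the truth and total signal as independent of it. If instead the difference were independent of total signal, the comparison would reverse. So no general gain in power follows, and at CV 0.2 the gap is one subject. Nor does the plan say that later sample sizes will use the SD of the raw difference.

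LI is not a complete cure. Under the step 3 assumptions at CV 0.5, noise floors totalling 25% to 100% of the mean signal leave LI misordering 4% to 9% of pairs. That is better than 15.7%, but not zero.

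A reader might infer more than the documents support:
- That subjects could be assigned to the wrong hemisphere, or that the group test is invalid. Common scaling does not change the sign, and the group test is not affected.
- That the analysis contradicts the Background. The Background is literature context built on a dipole model, whereas Source Imaging plans a distributed method. This is an omission, not a contradiction.
- That whole-hemisphere values will be used, or that nothing is excluded before averaging. The plan never says whole-hemisphere, and it does mark bad segments. Only exclusion of target epochs is absent.
- That the memory analysis or the 3.2 nAm cut-off is in error. Details are unstated, and the references may supply them.

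**Conclusion.** The point holds in a limited form. As written, individual dominance is an unnormalised difference. If activation is a source amplitude, its size depends on overall response strength, exactly and in proportion, while its direction does not. Degree of dominance is therefore not comparable between subjects, and an SD derived from it mixes asymmetry with signal strength. The practical size cannot be fixed from the documents: under the assumptions in step 3, signal strength accounts for 6% to 62% of the raw variance.

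For language, the window and region in the Background should be carried into the analysis, and the influence of target epochs should be checked. The motor and sensory effects are modest under the assumed values, and the motor effect is small in a posterior temporal region. This is a small feasibility pilot whose only specified test is unaffected, so the case for acting rests on the low cost and on the stated use of the data for planning later research.

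**What to change.** In Statistical Analysis, under Hemispheric dominance:
- Report LI = (L-R)/(L+R) beside the raw difference. State the amplitude scale, and either subtract the pre-stimulus baseline (noise) level or report it for each subject. If the cited references already define a normalised index, write that definition into the plan.
- For language, compute LI in the posterior temporal region over 150-700 ms, and show 200-700 ms as well so that the overlap with the early sensory interval is visible.
- Add a sensitivity analysis of the language LI on the 120 distractor epochs (the count assumes each target occurs once per block). Keep all epochs in the main average, apart from segments marked bad.

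As minor clarifications, state the window, trigger event and cortical regions for memory, and whether the 3.2 nAm cut-off enters dominance or only selects dipoles for display on the MRI. Deep structures lie outside the cortical surface model in Source Imaging, so naming them would need more than a wording change.

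The cost is SAP wording and a little more analysis on the same recordings. The sensitivity analysis has about 6% more noise; the main average loses no epochs to it. The downside is that LI is unstable when total activation is low, especially after baseline subtraction, which is one reason to keep the raw difference beside it.
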